17.4.2 Test of Superiority for IGA

The IGA will be dichotomized into “success” and “failure” with a Patient considered a success for those visits if the Investigator’s Global Assessment is at least 2 grades less than Baseline and “Clear” or “Almost Clear”. The analysis of the dichotomized IGA will be based on a logistic regression test with factors of treatment group and analysis center.

17.4.3 Test of Superiority for Secondary Efficacy and Control of Multiplicity

Appropriate descriptive statistics will be computed for all Secondary Efficacy parameters. Additionally, all inferential testing of percent change in lesions will follow the methods for the primary lesion count analyses. Methods corresponding to the analysis of IGA will be used to compare the proportion of patients in the E-BPO/E-ATRA Cream arm versus vehicle control achieving at least a 4-point reduction in pimples or in embarrassment scores from Baseline to Week 12.

The overall Type I error will be controlled by requiring the three co-primary efficacy endpoints to be statistically significant. Specifically, failure of either one of the primary efficacy endpoints will invalidate the statistical significance of the secondary efficacy endpoints.

Evaluation of the secondary efficacy variables will use a gated sequential procedure starting with the comparisons of the first step and proceeding onto the next step and etc. This stepwise process will be conducted for testing the secondary efficacy endpoints in order to control for multiplicity. These tests will be performed for only the ITT population. The testing process will terminate whenever a statistical test for a step is not significant. All subsequent tests for the remaining steps will be considered not significant. The order of testing is:

Step Number	Secondary Endpoint
1	Percent change from Baseline, in non-inflammatory lesion count at Week 12.
2	Percent change from Baseline, in inflammatory lesion count at Week 12.
3	Proportion of patients in the E-BPO/E-ATRA cream arm compared to vehicle control achieving at least a 4-point reduction on Item 1 (pimples) of the PRE-FACE from Baseline to Week 12.
4	Proportion of patients in the E-BPO/E-ATRA Cream arm compared to vehicle control achieving at least a 4-point reduction on Item 5 (embarrassment) of the PRE-FACE from Baseline to Week 12.
5	Absolute change from Baseline, in non-inflammatory lesion count at Week 8
6	Absolute change from Baseline, in inflammatory lesion count at Week 8.
7	Absolute change from Baseline, in non-inflammatory lesion count at Week 4.

8	Absolute change from Baseline, in inflammatory lesion count at Week 4.
---	--

17.4.4 Supportive Efficacy Analyses

Appropriate descriptive statistics will be computed for all Supportive Efficacy parameters. Additionally, all inferential testing will follow the methods for the co-primary variables wherein the continuous variables will parallel the lesion count analyses and the discrete variables will follow the analysis of the IGA.

17.4.5 Pooling Analysis

The clinical study will be conducted under a common protocol for each investigational site with the intention of pooling the data for analysis. Every effort will be made to promote consistency in study execution at each investigational site. The study is intended to be conducted in a manner such that a minimum of 5 Patients will be enrolled in each treatment arm for any Investigator. In the event that there are too few Patients in a treatment arm for an Investigator, then this Investigator's data will be combined to achieve the desired sample size minimum per arm. The combining of Investigator's data will be accomplished by taking the Investigator with the smallest enrollment and combining it with the Investigator with the largest enrollment. If there is a further need to combine data, then the data of the Investigator with the second smallest enrollment will be combined with the Investigator's data which had the second largest enrollment and so on. This process will continue for all Investigators who did not have a minimum of 5 Patients per treatment arm. The process of combining Investigator data that have insufficient Patients per treatment arm will result in redefining the groups of Investigators for the purposes of statistical analyses. These combined groups will be referred to as "analysis centers" in the statistical analyses based on ANCOVA and stratified logistic testing.

Prior to investigating the treatment effect within the analysis centers, the treatment effect within investigational site will be investigated to determine if the site-to-site variability is such that it could mask the analysis center effects. Thus, prior to pooling, change from baseline in inflammatory lesions and non-inflammatory lesions will be analyzed with an ANCOVA (unranked or ranked) with factors of treatment group, investigational site, and treatment group by investigational site interaction, and the respective baseline lesion count variable as a covariate. The dichotomized primary endpoint will be analyzed with a logistic regression with factors of treatment group, investigational site, and the interaction term of treatment group by investigational site. If any of the analyses are not computationally feasible due to some investigational sites having very few Patients enrolled, the low-enrolling investigational sites will be excluded from the analysis.

The consistency of treatment response will be investigated across the analysis centers subsequent to combining the data as described above. Statistical tests will be conducted to identify if there are extreme analysis centers that could affect the interpretation of common statistical and clinical conclusions. An analysis center by treatment interaction will be included in the primary variable analyses to test for parallel treatment effect at an alpha level of 0.10. Change from baseline in inflammatory lesions will be analyzed with an ANCOVA (unranked or ranked) with factors of treatment, analysis center, and treatment by analysis center interaction and the respective baseline lesion count variable as a covariate. For the purpose of testing consistency of treatment response, the

dichotomized IGA will be analyzed with a logistic regression procedure with factors of treatment, analysis center, and treatment by analysis center interaction. Further examination will follow for any variables that have a significant ANCOVA or logistic regression interaction term. In the event that the ANCOVA or logistic regression interaction (referred to henceforth as the "appropriate test") p-value is less than or equal to 0.10, a sensitivity analysis that excludes analysis centers with the extreme efficacy result will be performed to determine the robustness of the treatment effect. On the other hand, if the outcome of the appropriate test has a p-value greater than 0.10, then the conclusions from the pooled data will be considered to be free of the impact of extreme analysis centers.

The first step in conducting a sensitivity analysis is to identify the extreme analysis center or centers that contribute to the statistical significance of the appropriate test. The process involves submitting subsets of analysis centers to the appropriate test and observing the appropriate test p-value for the subset. Subsets with p-values greater than 0.10 for the appropriate test are considered homogeneous.

The search for an extreme analysis center begins by analyzing all subsets that can be created by excluding one analysis center. If one or more of the subsets result in an appropriate test p-value greater than or equal to 0.10, then the analysis center excluded from the subset with the largest p-value for the appropriate test is deemed to be the extreme analysis center.

If all appropriate test subset p-values are less than or equal to 0.10, then the process will analyze the appropriate test for all subsets that can be created by excluding two analysis centers. If one or more of these subsets generate appropriate test p-values larger than 0.10, then the analysis centers excluded from the subset with the largest appropriate test p-value are deemed the extreme analysis centers.

Thus, the process of identifying the extreme analysis centers will continue in a stepwise manner by first excluding one, then two, then three, etc., analysis centers until the appropriate test p-value exceeds 0.10.

Once the extreme analysis center or centers have been identified, then the treatment p-values of the remaining analysis centers will be computed. Inferences will be drawn from the treatment p-value, as well as any pertinent observations regarding the extreme analysis center or centers. Additionally, it is noted that this process excludes Patients from the analysis in a non-random manner and has an unpredictable impact on the power of the treatment effect test. In the event that the treatment effect of the remaining subset is not statistically significant, due consideration of the post-hoc aspects of the process will be given when the results are interpreted. Conclusions will be presented by the sponsor as appropriate to the findings of the sensitivity analysis.

17.4.6 Missing Efficacy Data Imputations

17.4.6.1 Lesion Count and PRE-FACE Variable Missing Data Imputation

Missing Week 12 data will be estimated by multiple imputation and subsequently analyzed. Missing lesion count data will be derived for the analysis using the method of Markov Chain Monte Carlo (MCMC) multiple imputation. Imputation will be conducted independently for each treatment group.

Multiple imputation and subsequent analysis will involve 3 distinct phases with these principal tasks:

1. Create a dataset of Patients, one for each treatment group, with observed values and those needing estimation by MCMC. The missing lesion count values in each dataset will be filled in using the MCMC method 5 times to generate 5 datasets. The resulting datasets for each treatment arm will be combined into one complete dataset for each imputation.

Syntax:

```
proc mi data=datain out=dataout seed=&seed. nimpute=5 <options>;  
  where trtpn=(1, or 2);  
  mcmc chain=multiple;  
  var baseline week2 week4 week8 week12;  
run;
```

2. For each complete dataset, the variable of interest for baseline minus the Week 12 value will be computed. Each complete dataset will be analyzed as specified for the particular analysis.
3. The results from these analyses will be combined into a single inference using SAS PROC MIANALYZE.

The following 4 random seeds have been pre-specified by using a random number generator:

- Inflammatory Lesion Counts; S6G5T-3: Seed = 813883085
- Inflammatory Lesion Counts; S6G5T-8 Vehicle: Seed = 2010726808
- Non-inflammatory Lesion Counts; S6G5T-3: Seed = 1326750493
- Non-inflammatory Lesion Counts; S6G5T-8 Vehicle: Seed = 1498908882

17.4.6.2 IGA Missing Data Imputation

A similar procedure will be used for the analyses based on proportion of IGA successes wherein the ANCOVA analysis is replaced with a logistic regression analysis. Specifically, missing Week 12 IGA values from which the dichotomized IGA is derived will be estimated by (MCMC). The pattern of missing observations in each treatment group cannot influence the missing value estimation in the other because the imputation is being conducted independently for each treatment group.

The missing Week 12 IGA values will be derived for the analysis using the method of Markov Chain Monte Carlo (MCMC) multiple imputation. Multiple imputation and subsequent analysis will involve 4 principal tasks:

1. Create a dataset, one for each treatment group, of Patients with observed values and those needing estimation by MCMC. The missing IGA values in each dataset will be filled in using the MCMC method 5 times to generate 5 datasets. The resulting datasets for each treatment arm will be combined into one complete dataset by imputation.

Syntax:

```
proc mi data=datain out=dataout seed=&seed. nimpute=5 <options>;  
  where trtpn=(1, or 2);  
  mcmc chain=multiple;  
  var baseline week2 week4 week8 week12;  
run;
```

2. For each complete dataset, the dichotomous success rate (clear or almost clear with a 2-point change from baseline) will be computed. The Week 12 estimated global values will be rounded to the nearest integer value prior to evaluating the success rate. Each complete dataset will be analyzed with a logistic regression with factors of treatment group and analysis center.

3. The results from these analyses will be combined into a single inference using SAS PROC MIANALYZE.

The following 4 random seeds have been pre-specified by using a random number generator:

- PRO Pimples Scores; S6G5T-3: Seed = 1597410322
- PRO Pimples Scores; S6G5T-3 Vehicle: Seed = 466920922
- PRO Embarrassment Scores; S6G5T-3: Seed = 288784276
- PRO Embarrassment Scores; S6G5T-3 Vehicle: Seed = 1746263137

17.4.7 Sensitivity Efficacy Analyses

17.4.7.1 Sensitivity analyses for absolute change in lesion count

The first sensitivity analyses for absolute change in lesion count (both inflammatory and non-inflammatory) will use a repeated measures ANCOVA, with treatment, analysis center, and visit (i.e., Week 2, Week 4 and Week 8) as independent factors and a covariate of baseline lesion count. In this analysis, data from all post-baseline visits will be included with no imputation for missing data.

The second sensitivity analyses will use the model based multiple imputation method to impute missing data for the absolute change in lesion counts at Week 12. Although the full details will be presented in the Statistical Analysis Plan (SAP), the multiple imputation will involve 4 principal tasks:

1. Missing values will be filled in 5 times to generate 5 complete datasets. The imputation model used will be an ANCOVA with factors of treatment group and analysis center, and a covariate of baseline lesion count (i.e., the imputation model will be the same as the analysis model). Appropriate modifications will be made should the analysis be based on a non-parametric method.
2. Each complete dataset will be analyzed with an ANCOVA with factors of treatment group, and analysis center, and a covariate of baseline lesion count.
3. Results from these analyses will be combined into a single inference.

The third sensitivity analysis will involve a tipping point analysis. Full details will be presented in the SAP.

17.4.7.2 Sensitivity analyses for IGA

The first sensitivity analysis for the dichotomized IGA success will use a repeated measures logistic regression model (generalized estimating equations), with dichotomized IGA success as the dependent variable and treatment, analysis center, and visit (i.e., Week 2, Week 4 and Week 8) as independent factors. In this analysis, data from all post-baseline visits will be included with no imputation for missing data.

The second sensitivity analysis will use the model based multiple imputation method to impute missing data for the dichotomized IGA data. Although the full details will be presented in the SAP, the multiple imputation will involve 4 principal tasks:

1. Missing values will be filled in 5 times to generate 5 complete datasets. The imputation model used logistic regression with factors of treatment group and analysis center (i.e., the imputation model will be the same as the analysis model).

2. Each complete dataset will be analyzed with a logistic regression a factors of treatment group and analysis center.
3. Results from these analyses will be combined into a single inference.

The third sensitivity analysis will involve a tipping point analysis. Full details will be presented in the SAP.

17.4.8 Subgroup Analyses

Subset analyses will be conducted for the ITT populations for the subgroups baseline global severity, gender, age, ethnicity, race, and geographic region. Age will be dichotomized to less than the median age of Patients and greater than or equal to the median age of Patients. An additional analysis will include age with categories of less than 18 and 18 to less than the median age and greater than or equal to the median age. Subset analyses will be conducted on the variables absolute change from baseline in inflammatory lesions at Week 12 as well as the dichotomized global severity score at Week 12. These analyses will contain only descriptive statistics.

17.5 Assessment of Safety

Safety will be evaluated by tabulations of AEs, the Investigator Cutaneous Safety Assessment rating of pigmentation, erythema, dryness and scaling; and the Patient assessment of Local Tolerability rating itching, burning and stinging will be presented with descriptive statistics at Baseline and at Weeks 2, 4, 8, and 12 for each treatment group. Frequencies and percentages for each outcome category will be included in these statistics. Mean values will be presented graphically by week and treatment group.

17.6 Adverse Events

All AEs occurring during the study will be recorded and classified on the basis of MedDRA terminology. Descriptions of AEs will include the date of onset, the date the AE ended (if applicable), the severity of the AE, the relationship to study product, the action taken regarding study product usage, the action taken to treat the AE, and the outcome. All reported TEAEs will be summarized by the number of Patients reporting AEs, system organ class, severity, seriousness, and relationship to study product. TEAEs are those AEs with an onset on or after the date of the first study product application.

AEs will be summarized by treatment group and severity. Each Patient will be counted only once within a system organ class or a preferred term by using the AEs with the highest severity within each category.

AEs will be summarized by treatment group and relationship to study product. Each Patient will be counted only once within a system organ class or a preferred term by using the AEs with the greatest relationship within each category.

Comparisons among treatment groups will be made by tabulating the frequency of Patients with one or more AEs (classified into MedDRA terms) during the study. The Fisher's Exact test will be used to compare the proportion of Patients in each treatment group who report any AE at a significance level of 0.05. The specific system organ classes and preferred terms analyzed will be those that are reported by at least one percent of the Patients in any treatment group.

All information pertaining to AEs noted during the study will be listed by Patient, detailing verbatim given by the Investigator, preferred term, system organ class, start date, stop date, severity, actions taken, and study product relatedness. The AE onset will also be shown relative (in number of days) to the day of initial dose of the randomized study product.

SAEs will be tabulated by Patient within treatment groups.

In addition, a list of Patients who discontinued from the study and a list of Patients who experienced SAEs will also be provided.

17.6.1 Vital Sign Measurements

Vital signs as well as changes from Baseline in vital sign measurements will be summarized with descriptive statistics for each treatment group at all applicable study visits.

17.6.2 Concomitant Medications

All previous therapies and concomitant medications will be classified based on terminology from the WHO Drug Dictionary. Previous therapies and concomitant medications data will be presented in data listings.

17.7 Sample Size Determination

The following power calculations are based on the observed Week 12 results of the Phase 2 study, SGT-65-02. This study was a six-arm trial including S6G5T-3 and Vehicle Cream in the treatment of acne vulgaris. Estimates from the S6G5T-3 arm were used in the power assessments. The anticipated randomization ratio is 2:1 for S6G5T-3 and S6G5T-8 Vehicle Cream, respectively. The computations were performed with nQuery Advisor Version 7.0 using a two-sided test with a statistical significance value of 0.05.

A sample size of 274 in the S6G5T-3 and 137 in the Vehicle Cream group (total of 411) has 99% power to detect a statistically significant difference in inflammatory lesions. The estimated absolute change from baseline in treatment means were -16.7 and -12.2 for S6G5T-3 and Vehicle Cream, respectively, with a common standard deviation of 10.0.

A sample size of 146 in the S6G5T-3 and 73 in the Vehicle Cream group (total of 219) has 99% power to detect a statistically significant difference in non-inflammatory lesions. The estimated absolute change from baseline in treatment means were -23.7 and -13.7 for S6G5T-3 and Vehicle Cream, respectively, with a common standard deviation of 19.0.

A sample size of 231 in the S6G5T-3 and 116 in the Vehicle Cream has group (total of 346) has 99% power to detect a statistically significant difference the proportion of Patients who have at least a 2-grade reduction at Week 12 from baseline in IGA and are Clear or Almost Clear. The estimated percentages with a 2-grade reduction at Week 12 from baseline in the IGA and Clear or Almost Clear are 33.3% and 12.6% for S6G5T-3 and Vehicle Cream, respectively.

Therefore, a total of 420 Patients has adequate power to demonstrate statistical significance of S6GT5-3 over S6GT5-8 Vehicle Cream for the lesion count endpoints as well as dichotomized IGA.

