4. INTRODUCTION

Acne vulgaris is a common condition of the pilosebaceous units of the skin (hair follicles and oil glands). Acne is the most common skin disorder in the United States, affecting 40-50 million Americans. Acne usually begins in puberty, but the condition is not restricted to any age group.

Approximately 85% of people between the ages of 12 and 24 experience at least minor, most often on the face, chest, and back [1]. Acne is caused by four major factors:

1. Production of oil by enlarged oil glands in the skin.
2. Blockage of the hair follicles that release oil.
3. Growth of bacteria, called *Propionibacterium acnes*, within the hair follicles.
4. Inflammatory/immune response to *P. acnes*.

The pathophysiologic features of acne suggest that combination therapy should be utilized as early as possible to simultaneously attack the multiple pathogenic factors of the condition [2]. Antimicrobials have been a mainstay of acne treatment for many years, having multiple mechanisms of action. The most important may be the ability of antibiotics to decrease the number of *P. acnes* in and around the follicle. They have a bacteriostatic effect on *P. acnes*, which prevents the bacteria from producing pro-inflammatory molecules [3].

In June 2017, Sol Gel completed a double blind, randomized, dose ranging Phase 2 trial for S6G5T-3 involving 726 adult Patients at thirty-six centers in the United States (SGT-65-02: A Phase 2, Randomized, Double Blind, Active and Vehicle Controlled, 12-Week Study Evaluating the Efficacy, Safety, and Tolerability of S6G5T-3 and S6G5T-1 for the Treatment of Acne Vulgaris). The Phase 2 trial had two co primary endpoints: success in Investigator Global Assessment (IGA) namely, a two-grade reduction in IGA on a scale of 0 to 4 (“clear”, “almost clear”, “mild”, “moderate”, “severe”) with “clear” or “almost clear” at Week 12; and a reduction in the mean inflammatory and non-inflammatory lesion count at Week 12 (end of trial). All Patients were 9 years of age or older with IGA of 3 or 4, 20 or more inflammatory lesions and 25 non-inflammatory lesions at enrollment. Patients were randomly divided into six groups of 119 to 122 Patients each and received a once daily dose, with one group receiving S6G5T-3 encapsulated benzoyl peroxide/encapsulated ATRA (E-BPO/E-ATRA 3%/0.1%), S6G5T-1

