(E-BPO/E-ATRA (3%/0.05%), E-ATRA 0.1%, E-ATRA 0.05%, E-BPO 3% and Vehicle Cream alone. S6G5T-3 demonstrated numerical superiority to the active component E-BPO 3% and vehicle for the co-primary endpoints (treatment success and lesion counts inflammatory) at the Week 12 visit but only matched efficacy for non-inflammatory lesions for E-ATRA 0.1%. The success rate for at Least 2-Grade Improvement and Clear or Almost Clear was 12.27%, 22.10%, 31.72% and 39.68% for Vehicle Cream, E-BPO 3%, E-ATRA 0.1% and S6G5T-3, respectively. The mean inflammatory change from Baseline was -11.5, -13.8, -14.9 and -16.9. for Vehicle Cream, E-BPO 3%, E-ATRA 0.1% and S6G5T-3, respectively. The mean non-inflammatory change from Baseline was -13.7, -16.2, -23.8 and -23.6 for Vehicle Cream, E-BPO 3%, E-ATRA 0.1% and S6G5T-3, respectively. S6G5T-3 each demonstrated statistical superiority ($p=0.006$ or less) to vehicle for the co-primary endpoints (treatment success, lesion counts both inflammatory and non-inflammatory) at the Week 12 visit.

In addition, S6G5T-3 were safe and well tolerated. The most common treatment-emergent adverse events (TEAEs) ($\geq 5\%$ incidence in any treatment group) were application site dryness, exfoliation and pain as well as upper respiratory infection. Cutaneous safety and tolerability assessment (erythema, scaling, pigmentation, itching, burning and stinging) by the Investigator showed that the proportion of Patients with these complaints tended to remain unchanged from Baseline over 12 weeks. On the other hand, based on self-assessments, a slightly greater proportion of Patients in the S6G5T-3 treatment groups had at least one higher post-baseline assessment of scaling, burning and stinging (mild) compared to vehicle. There were no apparent differences in mean changes from Baseline in any of the hematological and clinical chemistry test results in all treatment groups at Weeks 8 and 12. Most urinalysis test results were normal at Baseline and at Weeks 8 and 12. There were no clinically significant abnormalities in ECGs in the study.

In conclusion, both S6G5T-1 and S6G5T-3 demonstrate efficacy and safety in the treatment of acne vulgaris, however, S6G5T-3 showed additional benefit in achieving a greater proportion of treatment IGA success. Therefore, S6G5T-3 was selected as the “to be marketed formulation” and the active arm in this study.

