9. DETERMINATION OF SAMPLE SIZE

The following power calculations are based on the observed Week 12 results of the Phase 2 study, SGT-65-02. This study was a six-arm trial including S6G5T-3 and Vehicle Cream in the treatment of acne vulgaris. Estimates from the S6G5T-3 arm were used in the power assessments. The anticipated randomization ratio is 2:1 for S6G5T-3 and S6G5T-8 Vehicle Cream, respectively. The computations were performed with nQuery Advisor Version 7.0 using a two-sided test with a statistical significance value of 0.05.

A sample size of 274 in the S6G5T-3 and 137 in the Vehicle Cream group (total of 411) has 99% power to detect a statistically significant difference in inflammatory lesions. The estimated absolute change from Baseline in treatment means were -16.7 and -12.2 for S6G5T-3 and Vehicle Cream, respectively, with a common standard deviation of 10.0.

A sample size of 146 in the S6G5T-3 and 73 in the Vehicle Cream group (total of 219) has 99% power to detect a statistically significant difference in non-inflammatory lesions. The estimated absolute change from Baseline in treatment means were -23.7 and -13.7 for S6G5T-3 and Vehicle Cream, respectively, with a common standard deviation of 19.0.

A sample size of 231 in the S6G5T-3 and 116 in the Vehicle Cream has group (total of 346) has 99% power to detect a statistically significant difference the proportion of Patients who have at least a 2-grade reduction at Week 12 from Baseline in IGA and are Clear or Almost Clear. The estimated percentages with a 2-grade reduction at Week 12 from Baseline in the IGA and Clear or Almost Clear are 33.3% and 12.6% for S6G5T-3 and Vehicle Cream, respectively.

Therefore, a total of 420 Patients has adequate power to demonstrate statistical significance of S6GT5-3 over S6GT5-8 Vehicle Cream for the lesion count endpoints as well as dichotomized IGA.

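### Protocol 17.7 and SAP 9 claim 99% power for non-inflammatory lesions with 219 patients; the stated inputs give 95.5%, and 99% needs 303. The planned 420 is still adequate.

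*Protocol*

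**What the plan says.** Protocol 17.7 and SAP section 9 carry the same three power statements, computed in nQuery Advisor 7.0 "using a two-sided test with a statistical significance value of 0.05" and 2:1 allocation.

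- Non-inflammatory lesions: "A sample size of 146 in the S6G5T-3 and 73 in the Vehicle Cream group (total of 219) has 99% power". The inputs are "treatment means were -23.7 and -13.7 for S6G5T-3 and Vehicle Cream, respectively, with a common standard deviation of 19.0".
- Inflammatory lesions: "A sample size of 274 in the S6G5T-3 and 137 in the Vehicle Cream group (total of 411) has 99% power", with means of -16.7 and -12.2 and SD 10.0.
- IGA success: 231 and 116 patients for 99% power, with rates of 33.3% and 12.6%.

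Both sections conclude that 420 patients (280 and 140) are enough for all three co-primary endpoints. On the source of the inputs, the SAP states: "The following power calculations are based on the observed Week 12 results of the Phase 2 study, SGT-65-02".

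SAP section 4 describes the same Phase 2 study ("Patients were randomly divided into six groups of 119 to 122 Patients each") and lists its Week 12 results in the order vehicle, E-BPO, E-ATRA, S6G5T-3. For IGA: "The success rate for at Least 2-Grade Improvement and Clear or Almost Clear was 12.27%, 22.10%, 31.72% and 39.68" percent. For inflammatory lesions: "The mean inflammatory change from Baseline was -11.5, -13.8, -14.9 and -16.9".

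**The concern.** All the inputs to the non-inflammatory statement are printed beside it, so it can be recomputed without any assumption about the effect or the spread. It does not come out at 99%. The non-inflammatory count is one of three co-primary endpoints that must all be significant (protocol 17.4.3, SAP 8.1.8), so a wrong power figure for it matters to anyone who relies on the justification. If the fault lies in an input, a wrong planning SD or mean is also on record. The first question is whether the error reaches the total of 420.

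**Working it through.** **Method.** Two-sample t test with common SD and two-sided alpha 0.05. For difference D, SD s and group sizes n1 and n2, the noncentrality is δ = D / (s·√(1/n1 + 1/n2)) on n1 + n2 − 2 degrees of freedom. Power comes from the noncentral t. The normal approximation Φ(δ − 1.96) can be checked by hand.

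**1. Inflammatory statement, as a test of the method.** D = 16.7 − 12.2 = 4.5, s = 10.0, groups 274 and 137.
- δ = 4.5 / (10 × 0.1046) = 4.30, and Φ(2.34) = 99.0%.
- Noncentral t: 99.01% at 274/137 and 98.97% at 272/136.
- So 274/137 is the first 2:1 size to reach 99%, exactly as printed.

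**2. IGA statement.** With rates of 33.3% and 12.6%, a two-proportion test with continuity correction needs 116 on vehicle and 232 on active for 99%, against the printed 116 and 231. Without the correction, 231/116 gives 99.4%. The 99% label holds.

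**3. Non-inflammatory statement.** D = 23.7 − 13.7 = 10.0, s = 19.0, groups 146 and 73.
- δ = 10 / (19 × 0.1433) = 3.67, and Φ(1.71) = 95.7%.
- Noncentral t: **95.5%**, against 99% stated.

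**4. Size needed for 99%.**
- Normal approximation: vehicle n = 1.5 × (1.960 + 2.326)² × (19/10)² = 99.5, so 100 and 200, total 300.
- Noncentral t: 200/100 gives 98.99% and 202/101 gives 99.05%. The first size at 99% is **303**, which is 303 − 219 = 84 more than printed.
- 219 is not exactly the 95% size either: that is 144/72 = 216 (95.25%).

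**5. Other readings of the sentence.**

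| Reading | Result |
|---|---|
| One-sided 0.05, 146/73 | 97.8% |
| 219 patients split 1:1 | 97.2% |
| D = 9.9 (SAP section 4: -23.6 and -13.7), 146/73 | 95.1% |
| Rank test, assumed efficiency 0.955 | 303 / 0.955, about 318 patients for 99% |

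None reaches 99% with 219 patients, and the first two contradict the stated test and allocation. To get 99% from 146/73, the SD would have to be about 16.2 (D = 10.0) or the difference about 11.7 (SD 19.0).

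**6. Power at the planned 280/140, stated inputs.** The documents give no dropout rate for the sample size, and patients who discontinue are not replaced (protocol 12.2). The losses below are therefore assumed, and lost patients are treated as contributing nothing.

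| Loss | Non-inflammatory | Inflammatory | IGA |
|---|---|---|---|
| None | 99.9% | 99.1% | 99.8% |
| 10% | 99.8% | 98.4% | 99.6% |
| 30% | 98.9% | 95.2% | 98.2% |

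**7. Source of the planning values.**

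| Endpoint | Planning (17.7, SAP 9) | SAP section 4 |
|---|---|---|
| IGA success | 33.3 − 12.6 = 20.7 points | 39.68 − 12.27 = 27.4 points |
| Inflammatory | 16.7 − 12.2 = 4.5 | 16.9 − 11.5 = 5.4 |
| Non-inflammatory | 23.7 − 13.7 = 10.0 | 23.6 − 13.7 = 9.9 |

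The planning differences are the more cautious for IGA and inflammatory lesions, and very slightly less so for non-inflammatory lesions. One possible explanation is counted versus imputed data. At 119 to 122 patients per arm, 33.3% is 40/120 and 12.6% is 15/119, whereas 39.68% and 12.27% match no whole count (nearest 48/121 = 39.67% and 15/122 = 12.30%). The documents do not say.

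**The case against.** The case for leaving it alone is that no decision depends on this sentence. The total of 420 rests on the largest requirement, 411 for inflammatory lesions, and non-inflammatory power at 280/140 is 99.9%. That is correct, and it is why the point is minor. It does not make the printed figure right.

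It can also be said that the error is not confined to this sentence, because the IGA statement gives a total of 346 where 231 + 116 = 347. That slip is real, but it is an addition error and the IGA power figure holds. The power mismatch is confined to the non-inflammatory sentence.

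The count matching in step 7 is open to fair criticism: the size of each Phase 2 arm is not given, only the range, and the Phase 2 report is not available. It shows no more than that two sets of Phase 2 figures stand side by side unexplained. That is missing detail, and the main finding does not rest on it.

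Finally, the power figures at 280/140 with no loss assume complete data. Even with an assumed 30% loss, non-inflammatory power stays at 98.9%.

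**Conclusion.** The statement is wrong as written in both documents. With the printed inputs, 146 and 73 patients give 95.5% power, 3.5 points below the stated 99%; 99% needs 303 patients. This rests on the stated means, SD, 2:1 allocation and two-sided 0.05 level, and on a two-sample t test. The documents do not name the nQuery procedure, but that test reproduces the inflammatory statement exactly, and the normal approximation leads to the same conclusion. Whether the label or an input is at fault cannot be settled from the documents. The conclusion that 420 patients are adequate stands. Severity: minor.

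**What to change.** Look up the nQuery output for the non-inflammatory endpoint.

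- If the inputs are as printed, replace the sentence in protocol 17.7 and SAP section 9 with wording such as: *With these inputs, 146 and 73 patients (total 219) give about 95% power; 202 and 101 (total 303) give 99%; the planned 280 and 140 give 99.9%, assuming complete data.*
- If an input was copied wrongly, correct that input and leave the 99%.

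In the same edit, change the IGA total from 346 to 347, or correct the group sizes if the output shows otherwise. Add one sentence naming the Phase 2 analysis behind the planning values and saying why it differs from SAP section 4.

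The cost is wording only, with no change to enrolment, analysis or conclusions. The SAP can be updated until it is finalized before unblinding, and it takes precedence where the two documents differ (SAP section 2). The protocol text has to follow the IRB route in protocol 18.2 and could be corrected with the next amendment.
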